Vital Signs	x	х	х	х	х	х			Weight, temperature, diastolic and systolic blood pressure, pulse, pulse oximetry, and respiratory rate Q2W, at the EoT Visit, and at 30-day Safety FU. Only required at EoT if participant has not started a new antitumor treatment.
Physical Exam (PE)	х	х	x	Q6W	х	х			A complete PE will report findings in the irradiated area during all FU periods.
Evaluation of all Tissues in RT Area	x	х	x						

Study Period	RT Safe	ty FU Visits	and Avelumab 1	reatment	End o	of Treatme	nt (EoT)/FU	J	Notes
	RT Short-term Safety FU	RT Mid-term Safety FU	RT Long-term Safety FU	Avelumab Treatment	EoT	30-Day Safety FU	90-Day Safety FU ☎	Long- term FU	If participant discontinues avelumab prior to RT Long-term Safety FU, RT Long-term Safety FU can be performed by telephone.
Study Day (± Visit window)	43 (± 7)	99 (± 7)	351 (± 2)	n+14 d (± 2)	(Within 7 days of decision to discontinue)	30 days (± 5)	90 days (± 5)	(Q12W)	During on-treatment period, after Day 29, visits will be every 2 wks on days of avelumab infusions until EoT. All participants discontinuing study interventions for any reason must undergo an EoT Visit within 7 days after decision to discontinue study interventions, but (if possible) before any new antineoplastic therapy is started. The safety follow-up period will be 30 days (± 5 days) and 90 days (± 5 days) after the last dose of avelumab, see Section 4.1.1.3.
Premedication avelumab	х								Required only for first 4 avelumab infusions, as needed thereafter. See Section 6.5.5.
Avelumab	x	x	x	x					800 mg iv Q2W until PD. For post-PD treatment, see Section 6.6.6. For post-CR treatment, see Section 4.1.1.2.
ECOG PS	Х	Х	Х	Х	Х	Х			
Adverse Event Assessment	х	х	х	х	x	x	x	x	Continuously, at all RT safety FU, EoT, and Safety FU, ongoing treatment-emergent AEs should be evaluated. At Long-term FU, only needed if participant has not started a new antitumor treatment.
Concomitant Medication	X	х	x	X	×	X	X	X	
Hematology and Serum Chemistry	x	x	x	Q4W	x	х			Most recent complete hematology and core serum chemistry results must be available and reviewed prior to the administration of study interventions. See Appendix 6.
Dipstick Urinalysis				Q6W	х				Full urinalysis (dipstick + microscopic analysis) should be performed only at EoT. Otherwise, dipstick urinalysis Q6W. If dipstick urinalysis is abnormal, a full analysis should be performed.

Study Period	RT Safe	ty FU Visits	and Avelumab T	reatment	End o	of Treatme	nt (EoT)/FU	I	Notes

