Study Day (± Visit window)	43 (± 7)	99 (± 7)	351 (± 2)	n+14 d (± 2)	(Within 7 days of decision to discontinue)	30 days (± 5)	90 days (± 5)	(Q12W)	During on-treatment period, after Day 29, visits will be every 2 wks on days of avelumab infusions until EoT. All participants discontinuing study interventions for any reason must undergo an EoT Visit within 7 days after decision to discontinue study interventions, but (if possible) before any new antineoplastic therapy is started. The safety follow-up period will be 30 days (± 5 days) and 90 days (± 5 days) after the last dose of avelumab, see Section 4.1.1.3.
Premedication avelumab	x								Required only for first 4 avelumab infusions, as needed thereafter. See Section 6.5.5.
Avelumab	x	x	x	x					800 mg iv Q2W until PD. For post-PD treatment, see Section 6.6.6. For post-CR treatment, see Section 4.1.1.2.
Tumor Material				See notes					
Survival	x	x	x	x	x	х	х	x	All participants will be followed up for survival and use of subsequent anticancer therapy by phone every 12 wks until 1 year after last participant has received the last dose of study interventions or the last participant dies, whichever comes first.

2: phone call visit.

AE=adverse event, β-HCG=beta human chorionic gonadotropin, d=days, ECG=electrocardiogram, ECOG=Eastern Cooperative Oncology Group, EoT=End of Treatment Visit, FU=follow-up, iv=intravenous, mo=months, PD=progressive disease, QxW=every x weeks, RECIST=Response Evaluation Criteria in Solid Tumors, RT=radiotherapy, free T4=free thyroxine, TSH=thyroid-stimulating hormone, wk=week, WOCBP=women of childbearing potential.

Table 4 Schedule of Activities – Part FE (M3814 + Avelumab)

Study Period	Study Period Screening Treatment Period: M3814+ave				avelumab		End of T	reatment ((EoT)/FU	Notes		
- Study i criou	Screening	DL1	Peri	od				EoT	Safe	ety FU	Long-term FU	
Visit	-1	1	2	3	4	5	n				Q12W	During on-treatment period, after Day 29,

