3.2 Part B

Table 9 Study Objectives and Endpoints – Part B

Objectives	Endpoints (Outcome Measures)						
Primary							
To determine a safe, tolerable, RP2D and/or the MTD of M3814 when given in combination with avelumab and radiotherapy	Occurrence of DLTs from first treatment to planned final assessment at the end of DLT period at 4 weeks						

Objectives	Endpoints (Outcome Measures)						
Secondary							
Safety							
To evaluate the safety profile and tolerability of M3814 in combination with avelumab and radiotherapy	 Occurrence of treatment-emergent adverse events and treatment-related adverse events according to the NCI-CTCAE v 5.0, and serious adverse events Occurrence of abnormalities (Grade ≥ 3) in laboratory test values, markedly abnormal vital sign measurements, markedly abnormal physical examination measurements, clinically significant 						
	 abnormal ECG, marked changes in ECOG PS Incidence, severity and outcomes of RT-induced toxicity 						
Pharmacokinetics							
To characterize the pharmacokinetics of M3814 and avelumab when given in combination with radiotherapy	 Pharmacokinetic profile of avelumab in terms of pharmacokinetic parameter estimates, as feasible (e.g. Cmax, Cmln, Racc[Cmax], Racc[AUC] and t_{1/2}) 						
	 Pharmacokinetic profile of M3814 in terms of pharmacokinetic parameter estimates (C_{max}, t_{max}, C_{min}, C_{avg}, fluctuation index, AUC_{0-t}, AUC_{0-∞}, Racc[C_{max}], Racc[AUC], t_{1/2}, Vz/f, CL/f, and Λz) 						
Immunogenicity							
To evaluate the immunogenicity of avelumab in combination with M3814 plus radiotherapy.	Immunogenicity as measured by ADA						
Efficacy							
To evaluate the preliminary antitumor activity of M3814 when given in combination with avelumab and radiotherapy in participants with locally advanced and advanced solid tumors							
	 Tumor size measurement based on Investigator assessment according to RECIST v 1.1 from the first study interventions dose until confirmed PD or start of new cancer treatment 						
	Overall Survival						
Exploratory							
CCI							

[figure not shown]
Objectives							Endpoints (Outcome Measures)									
CCI																

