- Mucositis (mucosal inflammation), including oral mucositis (stomatitis) or esophagitis of Grade ≥ 3 lasting for ≤ 4 weeks after completion of the study treatments
- Stomatitis associated toxicities (e.g., swallowing dysfunction [odynophagia, dysphagia], decreased appetite, or weight loss due to difficulty or painful swallowing) of Grade ≥ 3 lasting for ≤ 4 weeks after completion of the study treatments
- Radiation dermatitis and associated toxicities of Grade ≥ 3 lasting for ≤ 4 weeks after completion of the study treatments
- For participants suffering from squamous cell carcinoma of head and neck and who receive RT in the head and neck region: the duration of feeding tube (FT) use (nasogastric tube, percutaneous endoscopic gastrostomy) should not define the severity of the toxicity (e.g., severe swallowing dysfunction, nausea, vomiting). A careful evaluation of the participant's symptoms by the Investigator at each visit is required in order to identify participants who are FT dependent (e.g., participants who refuse/avoid swallowing, etc).

At any time during the study, the SMC may identify as a DLT any adverse drug reactions (ADR) in participants treated with M3814 in combination with avelumab (Part A) and with avelumab and RT including in-field late radiation toxicities (Part B).

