7.3 Lost to Follow Up

A participant will be considered lost to follow-up if he or she repeatedly fails to return for scheduled visits and is unable to be contacted by the study site.

The following actions must be taken if a participant fails to return to the clinic for a required study visit:

- The site must attempt to contact the participant and reschedule the missed visit as soon as possible, counsel the participant on the importance of maintaining the assigned visit schedule, and ascertain if the participant wants to or should continue in the study.
- Before a participant is deemed "lost to follow up", the Investigator or designee must make every effort to regain contact with the participant: 1) where possible, make 3 telephone calls; 2) if necessary, send a certified letter (or an equivalent local method) to the participant's last known mailing address, and 3) if a participant has given the appropriate consent, contact the participant's general practitioner for information. These contact attempts should be documented in the participant's medical record.
- Should the participant continue to be unreachable, he/she will be considered to have withdrawn from the study.

Study Assessments and Procedures 8

- Study assessments and procedures and their timing are summarized in the Schedule of Activities.
- No protocol waivers or exemptions are allowed.
- Immediate safety concerns should be discussed with the Sponsor immediately upon occurrence or awareness to determine if the participant should continue or discontinue study intervention.
- · Adherence to the study design requirements, including those specified in the Schedule of Activities, is essential and required for study conduct.

- All Screening evaluations must be completed and reviewed to confirm that potential
 participants meet all eligibility criteria. The Investigator will maintain a Screening log to record
 details of all participants screened, to confirm eligibility, and if applicable, record reasons for
 Screening failure.
- Prior to performing any study assessments that are not part of the participant's routine medical care, the Investigator will obtain written informed consent as specified in Appendix 2 (Study Governance).
- Procedures conducted as part of the participant's routine medical care (e.g., blood count) and
 obtained before signing of the ICF may be used for Screening or Baseline purposes provided

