8.3 Adverse Events and Serious Adverse Events

The definitions of an AE and an SAE are in Appendix 4, as is the definition of an Adverse Event of Special Interest (AESI).

8.3.1 Time Period and Frequency for Collecting Adverse Event and Serious Adverse Event Information

The AE reporting period for safety surveillance begins when the participant is initially included in the study (date of first signature of informed consent/date of first signature of first informed consent) and continues until the last Long-term Follow-up Visit.

Any SAE assessed as related to study intervention must be recorded and reported, as indicated in Appendix 4, whenever it occurs, irrespective of the time elapsed since the last administration of study intervention.

The method of recording, evaluating, and assessing causality of AEs (including SAEs) and the procedures for completing and transmitting SAE reports are in Appendix 4.

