8.3.2 Method of Detecting Adverse Events and Serious Adverse Events

At each study visit, the participant will be queried on changes in his or her condition. During the reporting period, any unfavorable changes in the participant's condition will be recorded as AEs, regardless if reported by the participant or observed by the Investigator.

Complete, accurate and consistent data on all AEs experienced for the duration of the reporting period (defined below) will be reported on an ongoing basis in the appropriate section of the eCRF. All SAEs and all nonserious AEs of special interest must be additionally documented and reported using the appropriate Report Form as specified in Appendix 4.

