8.3.3 Follow-up of Adverse Events and Serious Adverse Events

AEs are recorded and assessed continuously throughout the study, as specified in Section 8.3.1 (Time Period and Frequency for Collecting Adverse Event and SAE Information) and are assessed for their outcome at the last Long-term Follow-up Visit. All SAEs ongoing at the last Long-term Follow-up Visit must be monitored and followed up by the Investigator until stabilization or until the outcome is known, unless the participant is documented as "lost to follow-up". Reasonable attempts to obtain this information must be made and documented. It is also the responsibility of the Investigator to ensure that any necessary additional therapeutic measures and follow-up procedures are performed. Further information on follow-up procedures is given in Appendix 4 (AEs: Definitions and Procedures for Recording, Evaluating, Follow-up, and Reports).

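### In Part B the Schedule drops adverse event assessment at the 12-weekly Long-term FU once new antitumor treatment starts, while Sections 8.3.1 to 8.3.3 make no such exception; a narrow class of late radiation toxicity may go unasked until Day 351

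*Protocol*

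**What the plan says.** The adverse event row of Table 3 (Protocol Section 1.3) asks for assessment without condition at the RT safety contacts (Days 43, 99 and 351), at End of Treatment, and at the 30- and 90-day Safety FU. For the 12-weekly Long-term FU it adds a condition: "At Long-term FU, only needed if participant has not started a new antitumor treatment". Tables 1 and 4 carry the same note for Parts A and FE.

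Section 8.3 is worded without that condition:

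- The reporting period in 8.3.1 starts at consent "and continues until the last Long-term Follow-up Visit".
- 8.3.2 says: "At each study visit, the participant will be queried on changes in his or her condition".
- 8.3.3 says: "AEs are recorded and assessed continuously throughout the study".

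The opening list of Section 8 adds: "Adherence to the study design requirements, including those specified in the Schedule of Activities, is essential". It does not say which text prevails if the Schedule and 8.3 differ.

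Contact itself continues. The Survival row of Table 3 says: "All participants will be followed up for survival and use of subsequent anticancer therapy by phone every 12 wks". The Concomitant Medication row is marked at Long-term FU with no new-therapy condition.

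**The concern.** A site whose participant has started another anticancer drug is told by 8.3 to ask about adverse events at the next 12-weekly contact and by Table 3 that it need not. Sites may resolve this differently.

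The consequence falls on Part B, where late radiation effects are of interest in their own right. "Incidence, severity and outcomes of RT-induced toxicity" is a secondary endpoint there (Section 3.2, Table 9), and under Section 6.6.3 the SMC may class a late in-field radiation toxicity as a DLT at any time. Appendix 8 places late effects beyond three months after RT and gives an average onset of six months for late radiation esophagitis. That lies between the Day 99 and Day 351 RT contacts, where the 12-weekly calls are the only other scheduled opportunity to ask once the 90-day call is past. The Day 351 contact may be a telephone call for someone who has stopped avelumab, so onset date and grade would then rest on recall.

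**Working it through.** The plan gives no figure to reproduce. The check is visit-day arithmetic on nominal days; the visit windows shift results by a few days.

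**Inputs.** RT contacts at Days 99 and 351 and the 90-day call after the last avelumab dose (Table 3); avelumab every 2 weeks from Day 1, so Days 1, 15 and 29 are the three DLT-period doses; Long-term FU every 12 weeks = 84 days; last RT fraction on Day 12 (Table 2); 1 month = 30.4375 days (SAP 9.1).

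**Upper bound on the gap.** Suppose new therapy starts before the first long-term call and the site applies the Table 3 note. With last avelumab dose on Day L, gap = 351 − max(99, L + 90).

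| Last dose (L) | 90-day call | Gap starts | Gap (days) |
|---|---|---|---|
| Day 1 | 91 | 99 | 351 − 99 = 252 |
| Day 29 | 119 | 119 | 351 − 119 = 232 |
| Day 57 | 147 | 147 | 351 − 147 = 204 |

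The full Day 99 to Day 351 interval needs L + 90 ≤ 99, that is L ≤ 9. On the dosing schedule only a last dose on Day 1 meets this.

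**Later new therapy, and the effect of the fix.** The protocol does not state the day from which the 12 weeks are counted. Assuming the 90-day call:

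| Last dose | Calls before Day 351 | Gap if new therapy starts after call 1 | Gap if after call 2 | Intervals between questions with the fix |
|---|---|---|---|---|
| Day 1 | 175, 259, 343 | 351 − 175 = 176 | 351 − 259 = 92 | 76, 84, 84, 8 |
| Day 29 | 203, 287 | 351 − 203 = 148 | 351 − 287 = 64 | 84, 84, 64 |
| Day 57 | 231, 315 | 351 − 231 = 120 | 351 − 315 = 36 | 84, 84, 36 |

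With the fix the longest interval is 84 days in all three cases.

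**Where late toxicity falls.** 6 × 30.4375 ≈ 183 days. Counted from Day 1 this is Day 184; counted from the end of RT on Day 12 it is Day 195. Both lie inside all three upper-bound gaps, 351 − 184 = 167 and 351 − 195 = 156 days before the next unconditional question.

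**What still reaches the database during the gap.**

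- SAEs assessed as related: reportable whenever they occur (8.3.1).
- Clinical Grade 4 and 5 events: always SAEs (Appendix 4).
- Toxicity already diagnosed: followed on a tailored schedule (Appendix 8) and to resolution (7.1).
- Toxicity that is treated: drugs and nondrug interventions are recorded to study completion, with reason for use and dates (Section 6.5), and the Concomitant Medication row applies at Long-term FU regardless of new therapy.

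The remainder is newly arising, nonserious toxicity that is largely untreated or transient, including in participants who die or are lost before Day 351.

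**Planned tables.** The SAP on-treatment period (9.1) ends at the earliest of 30 days after the last study intervention, the day before new anticancer drug therapy, and death. For the last doses shown, the gap starts at least 90 days after that dose, so events arising in it are outside the treatment-emergent tables in any case.

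**The case against.** **The note may waive less than it seems.** Its preceding sentence is about evaluating ongoing treatment-emergent events, so the condition could be read as applying only to those, with detection of new events left to 8.3. Section 8 also does not rank the Schedule above 8.3. The second remark is right, which is why this is a conflict between instructions and not a clear override. The first reading is strained, because the note qualifies the whole Adverse Event Assessment row. If it is what the sponsor means, the text should say so.

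**Late radiation toxicity has its own follow-up.** RT contacts at 1, 3 and 12 months are untouched by new therapy, and stopping adverse event collection once another anticancer drug is given avoids confounded events. Both are fair. They support keeping the waiver for other nonserious events, but not leaving the two texts in disagreement, nor leaving in-field events unasked on a call that is made anyway.

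**Treated toxicity would surface through concomitant medication.** This stands and narrows the point considerably.

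**The esophagitis example is weak.** Part B bars esophageal target lesions and excludes participants with more than 10% of the esophagus estimated to receive over 15 Gy. Accepted: the example shows timing and says nothing about expected frequency.

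**Late toxicity is mostly irreversible** (Appendix 8), so it would generally still be found at Day 351. This also stands, for those who reach Day 351. Entry requires only three months' estimated life expectancy, so some may not.

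**Conclusion.** The inconsistency between Table 3 and Sections 8.3.1 to 8.3.3 is real. Its practical effect is small and confined to Part B participants who stop avelumab early and start new therapy before Day 351. The unasked interval is at most 232 days for those who received all three DLT-period doses, 252 only if the last dose was Day 1, and shorter when avelumab or the long-term adverse event questions continue for longer. These are nominal bounds; the intermediate figures also rest on counting the 12-weekly calls from the 90-day call. Part B plans 6 to 24 participants, and the documents do not allow an estimate of how many would be affected.

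Three stronger readings are tempting and not supported. A reader might infer that every early stopper goes unasked from Day 99 to Day 351; the 90-day call rules this out for anyone dosed after Day 9. A reader might infer that all nonserious toxicity of Grade 3 or lower is lost; treated events are recorded with their reason for treatment, and lasting ones would generally be seen at Day 351. A reader might infer that the safety tables or the RT toxicity endpoint are undermined; treatment-emergent tables would not change, and the dedicated RT contacts remain. The supported conclusion is that some new, mild to moderate late radiation events may be missed, or recorded without a reliable onset date and grade.

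**What to change.** A cheap improvement in wording:

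1. Table 3, adverse event row: *At every 12-weekly Long-term FU call, ask about RT-related (in-field) AEs and related SAEs whether or not new antitumor treatment has started, and record the start date of that treatment. Other nonserious AEs need not be assessed after that date.*
2. Sections 8.3.1 to 8.3.3: state that, after new antitumor treatment starts, scheduled assessment at Long-term FU follows the Schedule for each part (Tables 1, 3 and 4), with the Part B radiation exception. Leave the SAE reporting rules as they are.
3. Optional, SAP 15.1.1: in the listing of all adverse events, flag Part B RT-related events with onset outside the on-treatment period, as 15.2.3 already does for SAEs.

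The cost is a short protocol edit, a few questions on two or three existing calls per affected participant before Day 351, and, if wanted, one listing flag. The downside is that some events reported after new therapy will be confounded by it; the recorded start date lets a reader see which.
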